8.2.3.4 Pregnancy

- Details of all pregnancies in female participants and, if indicated, female partners of male participants will be collected after the start of study intervention and until the completion of SFU.
- If a pregnancy is reported, the investigator should inform the sponsor within 24 hours of learning of the pregnancy and should follow the procedures outlined in [Appendix I](#).
- Abnormal pregnancy outcomes (e.g., spontaneous abortion, fetal death, stillbirth, congenital anomalies, ectopic pregnancy) are considered SAEs.
- Additional requirements for pregnancy testing during and after study intervention are located in [Appendix I](#).
- The investigator is responsible for review of medical history, menstrual history, and recent sexual activity to decrease the risk for inclusion of a woman with an early undetected pregnancy.

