 - If archived tumor tissue was obtained prior to progression on the last MKI with anti-RET activity, the patient should undergo a fresh tumor biopsy, if it is considered safe to perform, prior to treatment (optional).
9. Adequate hematologic status, defined as:
 - Absolute neutrophil count (ANC) $\geq 1.0 \times 10^9/L$ not requiring growth factor support for at least 7 days prior to treatment, and
 - Platelet count $\geq 75 \times 10^9/L$ not requiring transfusion support for at least 7 days prior to treatment, and
 - Hemoglobin (Hb) ≥ 9 g/dL not requiring transfusion support or erythropoietin for at least 7 days prior to treatment.
 10. Adequate hepatic function, defined as:
 - Alanine aminotransferase (ALT) or aspartate aminotransferase (AST) $\leq 2.5 \times$ the upper limit of normal (ULN) or $\leq 5 \times$ ULN with documented liver involvement (such as liver metastasis or a primary biliary tumor) and
 - Total bilirubin $\leq 1.5 \times$ ULN or $\leq 3 \times$ ULN with documented liver involvement (patients with Gilbert's Disease may be enrolled with prior Sponsor approval).
 11. Adequate renal function, with estimated glomerular filtration rate ≥ 30 mL/minute. Sites can use their own clinical standard for eGFR. If no clinical standard, below MDRD study equation can be used: $eGFR (mL/min/1.73 m^2) = 175 \times (S_{cr}/88.4)^{-1.154} \times (Age)^{-0.203} \times (0.742$ if female) $\times (1.212$ if African American) (SI units).
 12. Ability to swallow capsules and comply with outpatient treatment, laboratory monitoring, and required clinic visits for the duration of study participation.
 13. Willingness of men and women of reproductive potential to observe conventional and effective birth control for the duration of treatment and for 3 months following the last dose of study treatment; this may include barrier methods such as a condom or diaphragm with spermicidal gel.

Notes:

- A postmenopausal woman will be defined as having no menses for 12 months without an alternative medical cause. Male sterility will be defined as only men sterilized surgically. For male patients with a pregnant partner, a condom should be used for contraception. For male patients with a non-pregnant female partner of child-bearing potential and woman of child-bearing potential one of the following birth control methods with a failure rate of less than 1% per year when used consistently and correctly are recommended:

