 - a. Combined estrogen and progesterone containing hormonal contraception associated with inhibition of ovulation given orally, intravaginally, or transdermally
 - b. Progesterone-only hormonal contraception associated with inhibition of ovulation given orally, by injection, or by implant

- c. Intrauterine device (IUD)
 - d. Intrauterine hormone-releasing system (IUS)
 - e. Bilateral tubal occlusion
 - f. Vasectomized partner
 - g. Sexual abstinence
 - Birth control methods unacceptable for this clinical trial are:
 - a. Periodic abstinence (calendar, symptothermal, or post-ovulation methods)
 - b. Withdrawal (coitus interruptus)
 - c. Spermicide only
 - d. Lactational amenorrhea method
 - Male study participants should refrain from sperm donation during study treatment and up to 6 months following the last dose of selpercatinib.
14. Written informed consent and any local required authorization (e.g., Health Insurance Portability and Accountability Act in the US, European Union [EU] Data Privacy Directive in the EU) obtained from the patient/legal representative prior to performing any protocol-related procedures, including screening evaluations.
15. Cohorts 1 and 2: failed or intolerant to standard of care; see [Table 4-1](#) for Examples.

Table 4-1 Standard of Care Therapies for Cohort 1 and 2

| Cohort | Therapy |
|--|---|
| Cohort 1: RET Fusion-Positive Solid Tumor | 
NSCLC: platinum-based chemotherapy (or other chemotherapy if not eligible for platinum) or PD-1/PD-L1 immunotherapy or both
 
Thyroid: sorafenib, patients must also be radioactive iodine-refractory as appropriate
 
Colorectal: fluoropyrimidine-based chemotherapy, with or without anti-VEGF-directed therapy or anti-EGFR-directed therapy as appropriate for the disease
 
Pancreas: fluoropyrimidine-based, gemcitabine-based, or S-1 chemotherapy
 
Breast: anthracycline, taxane, HER2-directed therapy and/or hormonal therapy or other standard therapy appropriate for the disease
 
Other: prior standard therapy for the disease
 |
| Cohort 2: RET -mutant MTC | No approved SOC |

Abbreviations: EGFR-epidermal growth factor receptor; HER2-human epidermal growth factor receptor 2; MTC-medullary thyroid cancer; NSCLC-non-small cell lung cancer; PD-1-programmed cell death protein 1; PD-L1-programmed death-ligand 1; VEGF-vascular endothelial growth factor.

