Pregnancy (during maternal or paternal exposure to investigational product) does not meet the definition of an AE. However, to fulfill regulatory requirements any pregnancy should be reported following the SAE process to collect data on the outcome for both mother and fetus.

Suspected Unexpected Serious Adverse Reactions (SUSARs)

Lilly has procedures that will be followed for the identification, recording and expedited reporting of SUSARs that are consistent with global regulations and the associated detailed guidances.

Complaint Handling

Lilly collects product complaints on investigational products and drug delivery systems used in clinical studies in order to ensure the safety of study participants, to monitor quality, and to facilitate process and product improvements.

Patients will be instructed to contact the investigator as soon as possible if he or she has a complaint or problem with the investigational product so that the situation can be assessed.

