| CONTRACEPTIVES ^a ALLOWED DURING THE STUDY INCLUDE: |
| Highly Effective Methods^b That Have Low User Dependency |
| 
 • Implantable progestogen-only hormone contraception associated with inhibition of ovulation^c • Intrauterine device (IUD) • Intrauterine hormone-releasing system (IUS)^c • Bilateral tubal occlusion • Vasectomized partner • (Vasectomized partner is a highly effective contraceptive method provided that the partner is the sole sexual partner of the woman of childbearing potential and the absence of sperm has been confirmed. If not, an additional highly effective method of contraception should be used. Spermatogenesis cycle is approximately 90 days.) |
| Highly Effective Methods^b That Are User Dependent |
| 
 • Combined (estrogen- and progestogen-containing) hormonal contraception associated with inhibition of ovulation^c 
 ○ oral ○ intravaginal ○ transdermal ○ injectable • Progestogen-only hormone contraception associated with inhibition of ovulation^c 
 ○ oral ○ injectable • Sexual abstinence (Sexual abstinence is considered a highly effective method only if defined as refraining from heterosexual intercourse during the entire period of risk associated with the study intervention. The reliability of sexual abstinence needs to be evaluated in relation to the duration of the study and the preferred and usual lifestyle of the participant.) |
| 
a) Contraceptive use by men or women should be consistent with local regulations regarding the use of contraceptive methods for those participating in clinical studies.
 
b) Failure rate of <1% per year when used consistently and correctly. Typical use failure rates differ from those when used consistently and correctly.
 
c.) If locally required, in accordance with Clinical Trial Facilitation Group (CTFG) guidelines, acceptable contraceptive methods are limited to those which inhibit ovulation as the primary mode of action.
 
Note: Periodic abstinence (calendar, symptothermal, post-ovulation methods), withdrawal (coitus interruptus), spermicides only, and lactational amenorrhoea method (LAM) are not acceptable methods of contraception for this study. Male condom and female condom should not be used together (due to risk of failure with friction)
 |

Collection of Pregnancy Information

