Male participants with partners who become pregnant

- The investigator will attempt to collect pregnancy information on any male participant's female partner who becomes pregnant while the male participant is in this study. This applies only to male participants who receive selpercatinib.

- After obtaining the necessary signed informed consent from the pregnant female partner directly, the investigator will record pregnancy information on the appropriate form and submit it to the sponsor within 24 hours of learning of the partner's pregnancy. The female partner will also be followed to determine the outcome of the pregnancy. Information on the status of the mother and child will be forwarded to the sponsor. Generally, the follow-up will be no longer than 6 to 8 weeks following the estimated delivery date. Any termination of the pregnancy will be reported regardless of fetal status (presence or absence of anomalies) or indication for the procedure.

Female Participants Who Become Pregnant

- The investigator will collect pregnancy information on any female participant who becomes pregnant while participating in this study. Information will be recorded on the appropriate form and submitted to the sponsor within 24 hours of learning of a participant's pregnancy.
- The participant will be followed to determine the outcome of the pregnancy. The investigator will collect follow-up information on the participant and the neonate, and the information will be forwarded to the sponsor. Generally, follow-up will not be required for longer than 6 to 8 weeks beyond the estimated delivery date. Any termination of pregnancy will be reported, regardless of fetal status (presence or absence of anomalies) or indication for the procedure.
- While pregnancy itself is not considered to be an AE or SAE, any pregnancy complication or elective termination of a pregnancy will be reported as an AE or SAE. A spontaneous abortion is always considered to be an SAE and will be reported as such. Any post-study pregnancy related SAE considered reasonably related to the study intervention by the investigator will be reported to the sponsor as described in Section 8.3.2. While the investigator is not obligated to actively seek this information in former study participants, he or she may learn of an SAE through spontaneous reporting.
- Any female participant who becomes pregnant while participating in the study will discontinue study intervention or be withdrawn from the study.

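### Pregnancy collection stops at the safety follow-up visit, 56 to 70 days before the 3-month contraception period ends, and no end-of-treatment or follow-up procedure tests for or asks about pregnancy

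*Protocol*

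**What the plan says.** **Collection window.** Protocol 8.2.3.4 states that details of pregnancies in female participants and, if indicated, in partners of male participants "will be collected after the start of study intervention and until the completion of SFU". SFU is 28 days (+7) after the last dose in Sections 3.3 and 7.5, and 28 days (±7) in Table 7-1.

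**Contraception period.** For patients of either sex who could conceive or father a child, inclusion criterion 13 sets this requirement: "observe conventional and effective birth control for the duration of treatment and for 3 months following the last dose of study treatment". Its notes add: "Male study participants should refrain from sperm donation during study treatment and up to 6 months following the last dose of selpercatinib".

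**Reporting duty.** Section 8.2.3 says: "Pregnancy (during maternal or paternal exposure to investigational product) does not meet the definition of an AE". It continues that "to fulfill regulatory requirements any pregnancy should be reported following the SAE process to collect data on the outcome for both mother and fetus".

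**Appendix I.** For women: "The investigator will collect pregnancy information on any female participant who becomes pregnant while participating in this study". For men, it covers a "female partner who becomes pregnant while the male participant is in this study". Neither sentence mentions SFU.

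**Testing and questioning.** Table 7-1 (note m) schedules pregnancy tests at Screening and on Day 1 of each cycle. The EOT, SFU and LTFU cells of that row are empty. The lists in 7.4 (EOT) and 7.5 (SFU), the LTFU text in 7.6 and note gg contain no pregnancy test or question. Section 8.2.3.4 refers the reader to Appendix I for pregnancy testing during and after treatment, but Appendix I contains only definitions, contraceptive methods and reporting rules.

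**The concern.** The protocol sets 3 months after the last dose as the period in which conception should be avoided, yet its stated collection window closes at about one month. A site that follows 8.2.3.4 as written would not collect a pregnancy arising in most of the remaining period.

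Before and after that cut-off, nothing prompts the site to ask. The adverse event item at EOT and SFU does not do so by itself, because pregnancy is defined as not being an AE. Section 3.1 mentions safety during LTFU, but note ee ends AE and SAE recording at SFU.

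What is at stake is the completeness of a small but important piece of safety data. Two groups matter most: women who conceive late in the last cycle and recognise it only after SFU, and partners of treated men, for whom the protocol sets restrictions of 3 months (contraception) and 6 months (sperm donation).

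**Working it through.** The plan gives no figure of its own here, so the check is simple arithmetic followed by a comparison of the texts.

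**Inputs**
- SFU: day 21 to 35 after last dose (Table 7-1); day 28 to 35 under 7.5.
- Contraception period: 3 months (criterion 13), taken as 91 days. The SAP conversion gives 3 × 30.4375 = 91.3 days.
- Pregnancy test: Day 1 of each cycle, up to 2 days early (note m); cycles are 28 days.
- Sample size: approximately 75 (Section 3.6).
- Contraceptive failure: below 1% per year for the recommended methods (criterion 13 notes).

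**1. Contraception period left outside the 8.2.3.4 window** = 91 − SFU day
- SFU at day 35: 91 − 35 = 56 days (62%)
- SFU at day 28: 91 − 28 = 63 days (69%)
- SFU at day 21: 91 − 21 = 70 days (77%)

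**2. Time from last scheduled test to SFU** = days tested early + days from Day 1 to last dose + SFU day
- Shortest: 0 + 0 + 21 = 21 days
- Longest: 2 + 27 + 35 = 64 days

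This assumes that the last cycle was not prolonged by an interruption. It also leaves aside a patient who stops in Cycle 1, whose screening test may stand in for the Day 1 test.

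**3. Expected pregnancies in the gap** = 75 × 0.01 × gap/365, with all 75 patients treated as at risk (themselves or through a partner)
- 56 days: 75 × 0.01 × 56/365 = 0.115
- 63 days: 75 × 0.01 × 63/365 = 0.129
- 70 days: 75 × 0.01 × 70/365 = 0.144

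The result is proportional to the number at risk, which will be below 75, and to the failure rate. One per cent is not an upper limit on that rate, because criterion 13 also allows barrier methods such as a condom, or a diaphragm with spermicidal gel.

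**4. Does Appendix I close the gap?** It ties collection to being in the study. Section 3.2.2 ties the end of study to the last remaining patient's SFU visit (or withdrawal, loss to follow-up, death or transfer), which suggests that participation ends at SFU. Sections 3.3 and 7.6 treat LTFU as part of the study and its patients as still on study. The text therefore does not settle whether Appendix I reaches beyond SFU.

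**5. Does 8.2.3 close the gap?** It makes a pregnancy during maternal or paternal exposure reportable and sets no SFU limit. That duty works only once the site knows of the pregnancy, and no scheduled step brings it to light.

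**The case against.** The strongest case against is that this is a drafting gap with little consequence. Section 8.2.3.4 can be read as setting the period and Appendix I as giving the procedures once a pregnancy is reported, so the two need not collide. Section 8.2.3 already covers exposed pregnancies, abnormal outcomes are SAEs under 8.2.3.4, and 8.2.3.1 requires notification of related SAEs learned of later. Consent text and site forms are not available here, so what patients are told to report cannot be judged.

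Much of this stands, and it rules out several stronger readings that a reader might infer:

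- *That 8.2.3.4 and Appendix I flatly contradict each other.* Because of Section 3.2.2, the difference is an ambiguity.
- *That the protocol lets exposed pregnancies go unreported.* Section 8.2.3 says otherwise once they are known, and up to SFU there is a general duty to collect.
- *That the protocol's own figure, "Spermatogenesis cycle is approximately 90 days", fixes the exposure window for partners.* That sentence belongs to the note on vasectomized partners and is not a statement about drug exposure. The documents give no reproductive toxicity data from which such a window could be derived.
- *That women who conceive after SFU carry a material exposure risk.* Section 6.3.2 puts 5 half-lives at about 2 to 3 days, so this concern is small.

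What the objection does not answer is that the stated window is shorter than the protocol's own contraception period, that no EOT, SFU or LTFU procedure asks about pregnancy, and that the pointer to testing text leads to nothing.

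**Conclusion.** The point holds as a minor, inexpensive improvement to safety data. Under 8.2.3.4 as written, 56 to 70 of about 91 days of the required contraception period fall outside pregnancy collection. The last scheduled test is 21 to 64 days before SFU, and nothing at EOT, SFU or LTFU elicits a pregnancy. Whether Appendix I extends collection into LTFU is unclear.

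The expected number of missed pregnancies is about 0.1 or fewer at 1% per year, with the caveat that permitted barrier methods may fail more often. The conclusion rests on taking 3 months as 91 days and on using the protocol's contraception requirement as the benchmark; it does not depend on any claim about drug effects on sperm. ORR, its confidence interval and the sample size are not affected.

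**What to change.** 1. In both 8.2.3.4 and Appendix I, collect every pregnancy in a female participant, or in a male participant's partner, with estimated conception between first dose and 3 months after last dose, whenever it is reported. Defining the window by conception matters: a bare 3-month cut-off on report date would miss conceptions recognised late.
2. Keep any longer Appendix I duty for pregnancies that the site learns of while the patient is on study, so that alignment does not shorten collection. State whether LTFU counts as being on study for this purpose.
3. Add a pregnancy question (participant or partner) at SFU and at the first LTFU telephone contact on or after month 3. LTFU contacts are every 3 months ±1 month, so this is the second contact if the first falls early.
4. Either supply the post-treatment testing text that 8.2.3.4 says is in Appendix I, or delete the pointer. Correct the Appendix I reference to Section 8.3.2, which does not exist.

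The cost is amendment wording, with the IRB/IEC approval that any amendment needs (Section 10.1), and one or two questions at existing contacts. No new visit is needed, and no new test unless the sponsor chooses to supply the testing text in item 4.

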8.2.3.5 Cardiovascular and Death Events

Not applicable.

8.3 Treatment of Overdose

Refer to the IB and/or product label of selpercatinib for available information on the signs, symptoms, and treatment of overdose.

8.4 Pharmacokinetics

At the visits and times specified in the Schedule of Activities (Table 7-1), blood samples of approximately 2 mL each will be collected to determine the plasma concentrations of selpercatinib.

A maximum of 6 samples may be collected at additional time points during the study if warranted and agreed upon between both the investigator and sponsor. Instructions for the collection and handling of blood samples will be provided by the sponsor. The actual date and time (24-hour clock time) of each sampling and prior dose will be recorded.

For 12 subjects in intensive PK testing, PK test performed on C1D1: Up to pre-dose, and post-dose 1 hour (± 15 minutes), 2 hours (± 15 minutes), and 4 hours (± 15 minutes), 8 hours (± 30 minutes) and 12 hours (± 30 minutes), C1D8: Up to pre-dose, and post-dose 1 hour (± 15 minutes), 2 hours (± 15 minutes), and 4 hours (± 15 minutes) and 8 hours (± 30 minutes). For all enrolled subjects in PopPK testing, PK test performed on each cycle D1. Exact clock time (24h format) of sample collection and of dose administration should be recorded. Time of previous 3 doses should also be recorded.

Additional PK may also be assessed in patients when considered necessary by the Investigator to understand exposure in relationship to possible safety.

PK samples will be retained at a facility selected by Lilly for a maximum of 4 years after the last patient visit for the study.

8.5 Pharmacodynamics

Not applicable.

8.6 Biomarker

Biomarker research is performed to address questions of relevance to drug disposition, target engagement, variability of participant response (including safety), and clinical outcome. Sample collection is incorporated into clinical studies to enable examination of these questions through measurement of biomolecules including deoxyribonucleic acid (DNA), ribonucleic acid (RNA).

Tissue samples for biomarker research will be collected at the times specified in the Schedule of Activities (Section 1.3) where local regulations allow. It is possible that biomarker data for patients in the study has already been generated from samples that were collected and analyzed

prior to enrolling in this study. This may include pathology reports and data generated from genetic analyses. If available, these data may be requested from medical records for use. In addition, for all patients, an anonymized/redacted Molecular Pathology Report or other report(s) describing tumor *RET* (and other) alteration analysis should be submitted to the Sponsor, designee, or central laboratory.

All samples will be coded with the participant number. These samples and any data generated can be linked back to the participant only by the investigator site personnel.

Archived tumor tissue should be submitted for Cohort 1 and 2, either via tumor block (preferred) or $\sim 10 \times 5\mu\text{m}$ unstained slides. We may have extracted DNA and RNA that be obtained from the tissue samples for central lab *RET* eligibility testing or *RET* alteration confirmation. Lilly has a right to retain a portion of the submitted tissue. Archival blocks will be sectioned and returned to the study site or patients. Slides and tissue samples collected on-study will not be returned. If patients cannot provide sufficient tumor tissue sample, patients still can be enrolled after discussion between sponsor and investigator and get sponsor's approval. Patients who do not have sufficient archival tumor tissue available may undergo a fresh tumor biopsy, if it is considered safe to perform, prior to treatment.

Samples (including tumor sample and derivatives such as DNA and RNA) will be retained at a facility selected by Lilly for a maximum of 4 years after the last patient visit for the study, or for a shorter period if local regulations and ERBs impose shorter time limits. This retention period enables response to regulatory questions related to selpercatinib.

